5.3 LIFESTYLE CONSIDERATIONS

Enrolled participants may be patients who do not consume caffeine or those who are habitual caffeine users. A dedicated analysis plan will be used to test associations between habitual caffeine use and specific outcomes of interest (see **Section 9.4, Statistical Analyses**).

5.4 SCREEN FAILURES

Screen failures are defined as participants who consent to participate in the clinical trial but are not subsequently randomly assigned to the study intervention or entered in the study. Screen failure information will be provided to (1) ensure transparent reporting, (2) meet the Consolidated Standards of Reporting Trials (CONSORT) publishing requirements, and (3) respond to queries from regulatory

The Caffeine, Postoperative Delirium, And CHange IN Outcomes after Surgery-2 (CAPACHINOS-2) Study Protocol <2.0>

Version <2.0>
<14 December 2022>

authorities. Reportable information includes demography, screen failure details, eligibility criteria, and any serious adverse event (SAE).

5.5 STRATEGIES FOR RECRUITMENT AND RETENTION

Our research group has established a robust infrastructure for recruiting surgical patients for perioperative clinical trials.^{6,80} For example, our department recruited >20,000 surgical patients for the Michigan Awareness Control Study over a two-year period.⁸⁰ Our department then served as one of two leading sites in a multicenter trial for preventing postoperative delirium, and >100 patients were recruited in a two-year period (with many of the same outcomes and assessment tools proposed in this study).⁶ Our research team has also recruited hundreds of patients for various smaller-scale trials and observational studies over the past few years.^{20,81-86} This local infrastructure for clinical trial recruitment and enrollment is firmly established, as we coordinate with preoperative clinics at Michigan Medicine to maintain weekly recruitment. Thus, we do not anticipate issues with recruitment or retention.

Additionally, targeted efforts will be made to enhance participant diversity and include historically under-represented patient populations. Such recruitment will be facilitated through the University of Michigan Office of Health Equity and Inclusion. This department aims to increase representation of historically underrepresented and underserved communities. Additionally, the Michigan Institute for Clinical and Health Research has established relationships with local communities that include underrepresented populations in research. By working with these programs, our goal is to bolster participant diversity via targeted connection with the community.

6 STUDY INTERVENTION

6.1 STUDY INTERVENTION(S) ADMINISTRATION

6.1.1 STUDY INTERVENTION DESCRIPTION

Participants will be block randomized with a 1:1:1 allocation ratio (placebo: low-dose caffeine: high-dose caffeine) in a three-arm parallel design. Prepared intravenous syringe solutions of D5W (placebo) or caffeine citrate will be directly delivered to the operating room prior to the surgery of enrolled participants. For the next two postoperative mornings, the study drug will be given with scheduled, morning medications as administered and overseen by the research nurse (or physician assistant).

6.1.2 DOSING AND ADMINISTRATION

The study drug will be administered as an intravenous infusion, using an infusion pump, over 30 (±5) minutes beginning during surgical closure and on the first two postoperative mornings. Low-dose caffeine will consist of 1.5 mg/kg caffeine base, and high-dose caffeine will contain 3 mg/kg caffeine base; both caffeine drugs will be dissolved in 40 mLs of dextrose 5% in water. No dose or timing changes are anticipated, and the infusion will be administered over the entire 30 (±5) minutes. A research nurse or physician assistant will oversee the drug administration and monitor blood pressure (every 5 minutes), heart rate, heart rhythm (via 5-lead electrocardiography), and continuous pulse oximetry.

6.2 PREPARATION/HANDLING/STORAGE/ACCOUNTABILITY

6.2.1 ACQUISITION AND ACCOUNTABILITY

Caffeine citrate injection (Fresenius Kabi) or generic equivalent (if the Fresenius Kabi product is not available) will be purchased by the Research Pharmacy using the study funds. Study drugs will be prepared, stored, and dispensed per hospital research pharmacy guidelines and protocols (see 6.2.3 and

The Caffeine, Postoperative Delirium, And CHange IN Outcomes after Surgery-2 (CAPACHINOS-2) Study Protocol <2.0>

Version <2.0>
<14 December 2022>

6.2.4). Unused drugs will be sent back to the research pharmacy and discarded per pharmacy protocols and standards.

6.2.2 FORMULATION, APPEARANCE, PACKAGING, AND LABELING

Per manufacturer (Fresenius Kabi USA, LLC) package insert: Caffeine citrate injection is indicated for the treatment of apnea of prematurity (<https://dailymed.nlm.nih.gov/dailymed/drugInfo.cfm?setid=38b39044-737a-4247-a6c4-c86f5e92490e&audience=consumer>). Caffeine citrate injection, USP for intravenous administration is a clear, colorless, sterile, nonpyrogenic, preservative-free, aqueous solution adjusted to pH 4.7. Each mL contains 20 mg caffeine citrate (equivalent to 10 mg of caffeine base) prepared in solution by the addition of 10 mg caffeine anhydrous to 5 mg citric acid monohydrate, 8.3 mg sodium citrate dihydrate and Water for Injection, USP. Caffeine, a central nervous system stimulant, is an odorless white crystalline powder or granule, with a bitter taste. It is sparingly soluble in water and ethanol at room temperature. The chemical name of caffeine is 3,7-dihydro-1,3,7-trimethyl-1H-purine-2,6-dione. In the presence of citric acid it forms caffeine citrate salt in solution. Vials should and will be inspected visually for particulate matter prior to use.

6.2.3 PRODUCT STORAGE AND STABILITY

Caffeine citrate injection, USP, is stored according to manufacturer recommendations in 3 mL single-dose vials. The drug will be stored in the hospital research pharmacy in accordance with hospital pharmacy practice and guidelines. Caffeine citrate is stable at room temperature over a 24-hour period.⁸⁷

6.2.4 PREPARATION

The assigned caffeine citrate dose will be diluted in dextrose 5% in water to a total volume of 40 mL. These procedures will occur via standard Michigan Medicine Research Pharmacy protocols, procedures, and operations.

6.3 MEASURES TO MINIMIZE BIAS: RANDOMIZATION AND BLINDING

As previously described, participants will be block-randomized with a 1:1:1 allocation ratio (placebo: caffeine 1.5 mg/kg: caffeine 3 mg/kg). Randomization will also be stratified by age (<75 or ≥75 years old) and sex. Older age is a risk factor for delirium, with patients 75 years of age and older having particularly high risk.¹³⁻¹⁵ Response to caffeine may also differ based on sex.⁸⁸ Stratified randomization will thus help to balance these biologically relevant, prognostic variables and mitigate selection bias. Additionally, research teams, patients, clinicians, and analysts will remain blinded to the study drug intervention. Regression models will also include adjustments for relevant confounders, and baseline imbalances, as described in **Section 9, Statistical Considerations**. Blinding can be broken, if necessary, per the physicians caring for the subject to ensure subject safety.

6.4 STUDY INTERVENTION COMPLIANCE

The research teams will use a mandatory case report form (CRF) to indicate that the study drug was given. Furthermore, the beginning and end times of the study drug infusion will be recorded for each participant. Reasons for deviation (e.g., not administering the study drug, incorrect administration timing) will also be reported and reported.

6.5 CONCOMITANT THERAPY

The Caffeine, Postoperative Delirium, And CHange IN Outcomes after Surgery-2 (CAPACHINOS-2) Study Protocol <2.0>

Version <2.0>
<14 December 2022>

No other study drugs will be given. Participants will receive medications as clinically indicated by perioperative providers. Caffeine is metabolized via Cytochrome P450 1A2, and medications that inhibit, induce, or serve as substrates for this system may affect caffeine metabolism (<https://drug-interactions.medicine.iu.edu/MainTable.aspx>). Co-administration of these medications will be recorded and considered during data analysis.

6.5.1 RESCUE MEDICINE

Not applicable

7 STUDY INTERVENTION DISCONTINUATION AND PARTICIPANT DISCONTINUATION/WITHDRAWAL

7.1 DISCONTINUATION OF STUDY INTERVENTION

Discontinuation of the study drug may occur for the following reasons:

- Participant is found to not meet all eligibility criteria
- Adverse cardiac event (e.g., unstable arrhythmia)
- Adverse neurologic event (e.g., seizure)
- Additional adverse events (e.g., hypersensitivity, allergic reaction)
- Clinician caring for the patient has requested discontinuing the drug due to safety concerns
- Discontinuation at the discretion of the study- or site-PI for additional concerns

Discontinuation from caffeine administration does not necessarily mean discontinuation from the study, and remaining study procedures should be completed as indicated by the study protocol. If a clinically significant finding is identified after enrollment (i.e., adverse reaction to the study drug), the investigator or qualified designee will determine if any change in participant management is needed. Any new clinically relevant finding will be reported as an adverse event (AE). The study drug may be restarted if deemed safe and appropriate by both the (1) clinical team caring for the patient and the (2) site-PI of the respective study site.

The data to be collected at the time of study intervention discontinuation will include the following:

- Time of drug initiation and discontinuation
- Reason for discontinuation
- Person (e.g., clinician, investigator) who requested that the drug be stopped

7.2 PARTICIPANT DISCONTINUATION/WITHDRAWAL FROM THE STUDY

Participants are free to withdraw from participation in the study at any time upon request. Additionally, an investigator may discontinue or withdraw a participant from the study for the following reasons:

- Significant study intervention non-compliance
- If any clinical adverse event (AE), laboratory abnormality, or other medical condition or situation occurs such that continued participation in the study would not be in the best interest of the participant
- Disease progression which requires discontinuation of the study intervention
- If the participant meets an exclusion criterion (either newly developed or not previously recognized) that precludes further study participation

The CAffeine, Postoperative Delirium, And CHange IN Outcomes after Surgery-2 (CAPACHINOS-2) Study Protocol <2.0>

Version <2.0>
<14 December 2022>

The reason for participant discontinuation or withdrawal from the study will be recorded on the designated case report form (CRF). Participants who sign the informed consent form and are randomized but do not receive the study intervention may be replaced. For participants who sign the informed consent form, are randomized, receive the study intervention, and subsequently withdraw (or are withdrawn or discontinued from the study), these participants will not be replaced if they have completed the primary outcome assessment. If such a participant is withdrawn or discontinued prior to assessing the primary outcome, that participant will be replaced.

7.3 LOST TO FOLLOW-UP

There is a close proximity in time between study intervention (i.e., study drug infusion) and early postoperative assessments. This assessment will occur when the patient is still hospitalized early in the postoperative course. Thus, loss to follow-up is not anticipated to be a major concern for the primary outcome in this study. However, such loss may occur in certain scenarios, such as unplanned intensive care unit admission with patients remaining intubated postoperatively. Loss to follow-up will thus be reported in study flow diagrams and is accounted for in power calculations (see **Section 9, Statistical Considerations**).

8 STUDY ASSESSMENTS AND PROCEDURES

8.1 EFFICACY ASSESSMENTS

The specific timing of procedures/evaluations to be done at each study visit are outlined in **Section 1.3, Schedule of Activities (SoA)**. Details regarding major trial assessment measures are described in the following section.

Screening/Enrollment Visit

Screening visits will be performed during either preoperative clinic visits or on the morning of surgery. Trained research team members will make a determination of study eligibility based on medical chart review and concurrent discussion with potential participants. Screening forms will then be reviewed, confirmed, and signed by the study PI ([name]) anytime between the initial screening visit and surgical intervention. During this initial visit, baseline vitals will be taken and a physical exam will be performed by clinic and perioperative clinicians per clinical standards. Baseline research case report forms will be completed, as outlined in **Section 1.3, Schedule of Activities (SoA)**, by trained research team members.

Delirium Assessments

Delirium will be assessed using the long-form CAM, via in-person assessment, during hospitalization. The CAM strategy will be used to assess delirium severity,² and total delirium duration (days) will also be calculated.

Quality of Recovery

The patient-reported 15-item Quality of Recovery scale will be used.³ This scale has been chosen as a key secondary outcome assessment, as caffeine is postulated to reduce delirium and, potentially, headache, which may help with the recovery process. The scale will be administered preoperatively at baseline and on the second postoperative afternoon. Results will be ascertained and recorded via in-person assessment by the research team.

Agitation and Sedation

Given that caffeine enhances arousal, as described previously, caffeine may also prevent states of obtundation, particularly in the early postoperative setting given the possibility of residual anesthesia.

The Caffeine, Postoperative Delirium, And CHange IN Outcomes after Surgery-2 (CAPACHINOS-2) Study Protocol <2.0>

Version <2.0>
<14 December 2022>

The RASS⁴ will thus be used to assess for agitation (+2 to +4) or sedation (-2 to -5) each timepoint of delirium assessment except for preoperative baseline (where the RASS will not be administered).

Headache

Headache presence and severity will also be assessed (10-centimeter visual analog scale, VAS) at each delirium assessment timepoint. The rationale for this outcome is that perioperative caffeine administration has been demonstrated to reduce rebound headache, particularly in habitual caffeine users.^{25,54}

Opioid Consumption

Perioperative opioid consumption will be collected via electronic medical records and converted to oral morphine equivalents as we have previously described.⁶

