1.3 SCHEDULE OF ACTIVITIES (SOA)

	Screening/ Enrollment Visit Day -14 to +1	Day of Surgery Visit 1, Day 1	Visit 2 Day 2 POD1 AM	Visit 3 Day 2 POD1 PM	Visit 4 Day 3 POD2 AM	Visit 5 Day 3 POD2 PM	Visit 6 Day 4 POD3 AM	Visit 7 Day 5 POD3 PM	Day 30
Procedures									
Informed consent	X								
Demographics	X								
Medical history	X								
Randomization		X							
Administer study intervention ^a		X	X		X				
Concurrent medication review	X	X	X	X	X	X	X	X	
Physical exam	X	X	X	X	X	X	X	X	
Vital signs	X	X	X	X	X	X	X	X	
Height	X	X							
Weight	X	X							
Cognitive function	X								X
Delirium assessments	X	X	X	X	X	X	X	X	
RASS Score		X	X	X	X	X	X	X	
Quality of Recovery								X	
PONV		X		X		X			
Headache assessments	X	X	X	X	X	X	X	X	
Opioid consumption data	X	X	X	X	X	X	X	X	
Dietary caffeine intake	X	X	X	X	X	X	X	X	
Physical function	X								X
Safety outcomes		X	X	X	X	X	X	X	X
Hospital length of stay and disposition									X
Adverse event review and evaluation	X	X	X	X	X	X	X	X	X
Complete Case Report Forms (CRFs)	X	X	X	X	X	X	X	X	X

On the day of surgery, assessments will occur one hour after postanesthesia care unit admission. Postoperative day (POD) assessments will occur between 7:00 – 10:00 AM, and afternoon assessments will occur between 3:00 – 6:00 PM. Outcomes will be ascertained either via in-person data collection or chart review as outlined in **Section 8.1, Efficacy Assessments**. ^aA research nurse or physician assistant will oversee the drug administration and monitor blood pressure (every 5 minutes), heart rate, heart rhythm (via 5-lead electrocardiography), and continuous pulse oximetry. ^bSee **Sections 8.2 and 9.4.4** for safety outcomes and assessments. Of note, primary and secondary outcomes are primarily reported in this table. Lastly, the 30-day visit can be conducted virtually and/or by telephone as well.

The Caffeine, Postoperative Delirium, And CHange IN Outcomes after Surgery-2 (CAPACHINOS-2) Study Protocol <2.0>

Version <2.0>
<14 December 2022>

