3 OBJECTIVES AND ENDPOINTS

OBJECTIVES	ENDPOINTS	JUSTIFICATION FOR ENDPOINTS
Primary		
To determine whether intravenous caffeine reduces the incidence of postoperative delirium	--The primary endpoint is delirium, as measured via long-form Confusion Assessment Method (CAM), obtained one hour after PACU admission and twice daily for the first three postoperative days. The CAM will be complemented by a validated chart review method ^{65,66} to mitigate missing delirium assessments.	The CAM is the most widely used measure for identification of delirium worldwide, validated in >22 studies with sensitivity and specificity of >90%. ^{1,67,68}
Secondary		
To determine whether caffeine reduces delirium severity	-- A secondary endpoint will be delirium severity, as measured via the same long-form CAM (CAM-S score).	CAM-S is a continuous scoring metric based on the long-form CAM (scored 0-19, 19 = highest severity). The CAM-S demonstrates high inter-rater reliability (0.88 – 0.92) and strong correlation with important clinical outcomes, including hospital length of stay, cognitive and functional decline, discharge disposition, and mortality. ²
To determine whether caffeine reduces delirium duration	-- An additional secondary endpoint related to delirium will be delirium duration, as measured by the cumulative number of days (n) with a positive delirium screen.	Delirium duration is associated with poor hospital outcomes. ⁶⁹

The Caffeine, Postoperative Delirium, And CHange IN Outcomes after Surgery-2 (CAPACHINOS-2) Study Protocol <2.0>

Version <2.0>
<14 December 2022>

OBJECTIVES	ENDPOINTS	JUSTIFICATION FOR ENDPOINTS
To determine whether intraoperative caffeine improves patient-reported quality of recovery	-- Patient-reported 15-item Quality of Recovery score, ³ which will be assessed in the afternoon on postoperative day two.	The original Quality of Recovery ³³ scale has been used for 20 years in perioperative clinical trials research. Extensive validity, ⁷⁰ reliability, ⁷⁰ and minimal clinically important difference data ³⁵ have been published. This scale was also recently endorsed by the Standardized Endpoints in Perioperative Medicine Initiative. ⁷¹ Caffeine is postulated to ameliorate pain and postoperative confusion, which are each independently associated with poor recovery on this scale. ³⁴

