9.4.3 ANALYSIS OF THE SECONDARY ENDPOINT(S)

For secondary endpoints, a similar GEE-based approach will be used. Within- and between- group comparisons will be analyzed based on coefficients in the model. This approach also allows for flexibility with missing data. Unstandardized beta coefficients will be presented with 95% confidence intervals and p-values (<0.05 will be considered statistically significant).

For non-repeated continuous measures (e.g., delirium duration, cumulative opioid consumption) and binary outcomes (e.g., postoperative delirium, headache), we will use the same GEE modeling approach. All GEE models will use the empirical parameter estimates with an exchangeable correlation matrix. As indicated previously, models will adjust for baseline cohort imbalances. Additionally, for Quality of Recovery and headache severity, the differential effect of habitual caffeine consumption and group will be tested. This will be tested via interaction term of habitual caffeine consumption with caffeine group (placebo, low-dose caffeine group, high-dose). The daily number of caffeinated beverages will be recorded for each participant, and the resulting distribution will be analyzed and used to inform the most appropriate categorization of habitual caffeine users (e.g., non-users, low-dose, high-dose, etc.).

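### The schedule of activities places the Quality of Recovery score on POD3 afternoon with no baseline, whereas Sections 3 and 8.1 set it at POD2 afternoon and 8.1 adds a preoperative baseline

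*Protocol*

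**What the plan says.** Three places in the protocol fix the timing of the 15-item Quality of Recovery score.

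- **Section 3 (Objectives and Endpoints)** defines the secondary endpoint as the score "which will be assessed in the afternoon on postoperative day two". It mentions no baseline.
- **Section 8.1 (Efficacy Assessments)** calls the scale a key secondary outcome and states: "The scale will be administered preoperatively at baseline and on the second postoperative afternoon".
- **Section 1.3 (Schedule of Activities)** has a row "Quality of Recovery" with one mark only, under "Visit 7 Day 5 POD3 PM". The cells under Screening/Enrollment and under "Visit 5 Day 3 POD2 PM" are empty.

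Two statements give the schedule authority. Section 8.1 opens with "The specific timing of procedures/evaluations to be done at each study visit are outlined in" and then names Section 1.3. The note under the schedule says that "primary and secondary outcomes are primarily reported in this table".

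**The concern.** The table and the text give different instructions for the same endpoint, on both the postoperative day and the baseline. The schedule is the page that staff work from at the bedside, and Section 8.1 directs them to it for timing. The same section says that baseline case report forms are completed as the schedule outlines, so the missing Screening mark could lead directly to a missing baseline.

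A team that follows the table would apply the right instrument on a day other than the one that defines the endpoint. The study drug is last given on the morning of POD2 (Sections 4.3 and 6.1.2). A POD2 afternoon score is therefore taken on the day of the last infusion, and a POD3 afternoon score on the day after. These are two different endpoints. A preoperative score that was not taken cannot be obtained later.

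**Working it through.** The protocol gives no figure to reproduce here. The check sets the passages side by side and tests whether the position of the mark could come from the way the table was read from the PDF.

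**1. Time points by source**

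| Source | Preoperative baseline | POD2 PM (Visit 5) | POD3 PM (Visit 7) |
|---|---|---|---|
| Section 3 | not mentioned | yes | no |
| Section 8.1 | yes | yes | no |
| Section 1.3 | no mark | no mark | marked |

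Sections 3 and 8.1 agree on the postoperative day, and the schedule is the outlier. The baseline rests on Section 8.1 alone.

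**2. Is the mark displaced by a column shift?** The header and each of the seven rows checked have ten fields (a label plus nine visit columns). Three of these rows have timing that the text states separately:

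| Row in 1.3 | Marks fall on | Text | Agree? |
|---|---|---|---|
| Study drug | day of surgery, POD1 AM, POD2 AM | 4.3 and 6.1.2: surgical closure and the first two postoperative mornings | yes |
| PONV | day of surgery, POD1 PM, POD2 PM | 8.2: PACU, then the afternoons of POD1 and POD2 | yes |
| RASS | day of surgery through POD3 PM, no Screening mark | 8.1: every delirium assessment except the preoperative one | yes |
| Quality of Recovery | POD3 PM only | 3 and 8.1: POD2 PM; 8.1 adds baseline | **no** |

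The table as a whole is aligned. Moreover, the row carries one mark while Section 8.1 needs two administrations, so no placement of a single mark would satisfy the text.

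**3. Distance between the two time points.** The note to the schedule puts every afternoon assessment at 3:00–6:00 PM, a window 3 hours wide. The same window one day later is 24 hours away, give or take the width of the window:

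- shortest gap: 24 − 3 = 21 hours
- longest gap: 24 + 3 = 27 hours

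**4. Day label in the same column.** Day of surgery is Day 1, both POD1 visits are Day 2, and both POD2 visits are Day 3, so the day number is POD + 1. POD3 AM follows this rule (3 + 1 = Day 4), but POD3 PM is labelled Day 5. Both POD3 visits fall on one calendar day, so the Visit 7 label is a second slip in the column that holds the mark.

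**5. What a baseline could add to precision (for the optional step only).** With correlation ρ between baseline and postoperative score, and no other covariates, adjustment multiplies the residual variance by 1 − ρ². The protocol gives no ρ, so a range of 0.3 to 0.5 is assumed:

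- ρ = 0.3: 1 − 0.09 = 0.91, a 9% reduction
- ρ = 0.5: 1 − 0.25 = 0.75, a 25% reduction

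These are upper values over that range. With other covariates in the model, the gain depends on the partial correlation and may be smaller. They describe the value of using a baseline and do not measure the effect of scoring on POD3 instead of POD2.

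**The case against.** The best defence is that this is one misplaced mark in a summary table. The trial is single-center, one team works from the whole protocol, and two sections state POD2 afternoon. The team may well be collecting the score on the intended day. That is fair as a statement about likelihood, and it is why the first step is to find out what has been done. It does not remove the contradiction, because Section 8.1 hands the question of timing to the schedule.

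It is also true that the baseline is stated in one place only, so the conflict over the baseline is between Sections 8.1 and 1.3, with Section 3 silent.

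Three stronger readings are tempting, and the document does not support them.

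- **A POD3 score would lose the patients who recover fastest.** Eligibility requires a planned stay of at least 72 hours, and the primary delirium assessment is scheduled at the same POD3 PM visit. Earlier discharge is possible, but no rate is given, and nothing shows who would leave.
- **The score changes quickly between POD2 and POD3.** The protocol gives no course over time for this scale. The point does not need one: the endpoint is defined on one day and scheduled on another.
- **Secondary models adjust only for variables that happen to be imbalanced.** Section 9.4.3 does say "As indicated previously, models will adjust for baseline cohort imbalances", but it also calls for an approach similar to the primary model, and Section 9.4.2 gives that model a priori covariates. A full covariate list for each secondary endpoint may properly sit in the SAP, which is not shown.

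**Conclusion.** The contradiction stands, on both the postoperative day and the baseline. If the schedule were followed to the letter, the key secondary score would be taken 21 to 27 hours after its defined time point and no participant would have a baseline. That is the worst case. The protocol does not show which instruction the team follows in practice. Nor does it allow the effect on the treatment comparison to be quantified, since it gives no POD2 and POD3 scores.

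Confidence in the contradiction itself is high. It rests on the column positions as read from the schedule, which agree with the text in the other rows checked. The matter should be corrected, but its reach is limited to one secondary endpoint. The primary delirium endpoint and the sample size are untouched.

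**What to change.** 1. Confirm from the case report forms which afternoon has been scored so far and whether a preoperative score was taken. Record any participants scored on a different day from the defined one.
2. Reconcile Section 1.3 with Sections 3 and 8.1: move the Quality of Recovery mark from Visit 7 to Visit 5 (POD2 PM), and add a mark at Screening.
3. Correct the day label of Visit 7, so that POD3 AM and POD3 PM carry the same day number.
4. Optional: once the baseline is collected, name the baseline Quality of Recovery score as a covariate for this endpoint in Section 9.4.3, unless the SAP already does so.

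Steps 2 and 3 are corrections to one table, and step 4 is one sentence. Step 1 takes a check of existing records. No extra visit is needed, since both visits already exist. If the baseline has not been collected so far, it can be secured only for participants not yet operated on, so the correction should not wait.
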